3.1.2 Definition of baseline

The main objectives of the study are to look at the safety and efficacy over 104 weeks, therefore the baseline definition is as defined in Section 3.1.1 of the SAPs of the predecessor studies and detailed below.

In general, the last non-missing measurement on or prior to the date of randomisation in the predecessor studies will serve as the baseline measurement for efficacy variables. If there is no value on or prior to the date of randomisation, then the baseline value will not be imputed, and will be set to missing.

In general, the last non-missing measurement prior to first dose of study treatment in the predecessor studies will serve as the baseline measurement for safety variables. If there is no value prior to first dose of study treatment, then the baseline value will not be imputed, and will be set to missing.

Where unscheduled/repeat assessments are relevant and exist for any subject at a particular visit they will also be considered in the baseline definitions, provided they remain prior to the date of randomisation (efficacy) or the date of first dose of study treatment (safety) in the predecessor studies.

For safety variables (vital signs, weight/BMI, haematology, clinical chemistry, urinalysis, 12-lead ECG), baseline will be defined as the latest non-missing assessment prior to first dose in the predecessor studies. If no time is recorded for an assessment, and the assessment takes place at the randomisation visit, this will be assumed to be a pre-dose assessment.

3.1.3 Absolute change from baseline

Absolute change from baseline is defined as (post-baseline value - baseline value).

If either the post-baseline value or the baseline value is missing, then the absolute change from baseline will also be missing.

Unless otherwise specified, "change from baseline" is assumed to be the absolute change from baseline.

3.1.4 Reversibility

Percentage reversibility is defined as follows, for pre-BD and post-BD measurements taken on the same date:

 $%Reversibility = [(Post-BD FEV_1 - Pre-BD FEV_1)/Pre-BD FEV_1] \times 100\%$

The FEV₁ post-BD measurement in the reversibility derivation is the measurement after up to 4 SABA inhalations.

3.1.5 Study periods

The following study periods are defined for analysis purposes:

Enrolment / Run-in period: starting on the date of the first study procedure and for D5180C00007, ending one day prior to randomisation in D5180C00007 (for randomised subjects), and for D5180C00009, ending one day prior to the start of the optimization period (Visit 2) (for randomised subjects) or on the date of the last study procedure (for screening failures). If any subject is re-screened in the predecessor studies, the latest available screening will be used for this purpose.

Optimization period (for D5180C00009 only): starting on the date of the first visit in the optimisation period (Visit 2) in the predecessor study and ending one day prior to randomisation in D5180C00009 (for randomised subjects). If any subject is re-screened, the latest available screening will be used for this purpose.

Planned treatment period (on-treatment and off-treatment): starting on the date of randomisation in the predecessor study (efficacy) / date of first dose of IP (safety) and ending on the minimum (date of the Week 104 visit, date of study withdrawal, day prior to start date of another biologic that impacts asthma control should this occur) for subjects enrolling into the LTE study, or ending on the minimum (date of the Week 52/48 visit, date of study withdrawal) otherwise.

On-treatment period: starting on the date of randomisation in the predecessor study (efficacy) / date of first dose of IP (safety) and ending on the minimum (date of last dose of IP + 33 days, date of death, date of study withdrawal, day prior to start date of another biologic that impacts asthma control should this occur).

Post-treatment/Follow-up period: starting one day after the end date of the on-treatment period and ending on the study completion or withdrawal date (this will be the later date if a subject completes the predecessor study and enrols in the LTE study).

On-study period (planned treatment and follow-up): starting on the date of randomisation in the predecessor studies (efficacy) / date of first dose of IP (safety) and ending on the study completion or withdrawal date (this will be the later date if a subject completes the predecessor study and enrols in the LTE study).

3.1.5.1 Time periods

In addition to the study periods defined above in Section 3.1.5, a predecessor period, LTE period, and period will be defined as subsets of the study periods. Data collected at EOT Week 52/48 visit in the predecessor studies will be regarded as during the predecessor period even if this data is recorded on the same day as the randomisation/first dose of IP during the LTE study. Note due to the difference in predecessor study durations, the predecessor period for data from D5180C00007 will be approximately 52 weeks and will be approximately 48 weeks for data from D5180C00009. Similarly, the LTE period will be approximately 52 weeks for D5180C00009.

Subjects from D5180C00009 will only enter approximately 12 weeks of FU period.

For most cases, the predecessor EOT visit, the enrolment visit of the LTE study, and the first dose of the LTE study occur on the same day. However, if subjects had a delay between the predecessor EOT visit and the first dose of IP in the LTE study, the predecessor period definitions below include all data up to the day of the first dose of IP in the LTE study. Likewise, the LTE period definitions below will start from the day of first dose of IP in the LTE study. If a subject had the enrolment visit of the LTE study but received no dose of IP afterwards, it was only counted in the predecessor periods.

Predecessor period:

- Planned treatment period: starting on the date of randomisation in the predecessor study (efficacy) / date of first dose of IP (safety) and ending on the enrolment visit in LTE study for subjects enrolling into the LTE study or ending on the minimum (date of the EOT visit in the predecessor study, date of study withdrawal in the predecessor study, day prior to start date of another biologic that impacts asthma control should this occur) for subjects not enrolling into the LTE study.
- On-treatment period: starting on the date of randomisation in the predecessor study (efficacy) / date of first dose of IP (safety) and ending on the enrolment visit in LTE study for subjects enrolling into the LTE study or the minimum (date of last dose of IP in the predecessor study + 33 days, date of death, date of study withdrawal, day prior to start date of another biologic that impacts asthma control should this occur) for subjects not enrolling into the LTE study.
- On-study period: starting on the date of randomisation in the predecessor studies (efficacy) / date of first dose of IP (safety) and ending on the enrolment visit in LTE study for subjects enrolling into the LTE study or ending on the study completion or withdrawal date in the predecessor study for those subjects not enrolling into the LTE study.

LTE period:

Note: LTE period is different from LTE study. LTE period includes the 12-week safety follow-up (for those who do not enrol into the period) but does not include period; whereas the LTE study (DESTINATION) includes period.

- **Planned treatment period:** starting on the day of the enrolment visit in the LTE study and ending on the date of the planned treatment period as defined above in Section 3.1.5.
- On-treatment period: starting on the day of the enrolment visit in the LTE study and ending on the date of the on-treatment period as defined above in Section 3.1.5.
- On-study period: for subjects who do not enter the starting on the day of the enrolment visit in the LTE study and ending on the date of the on-study period as defined above in Section 3.1.5. This end date will be the study completion date (Week 116) or early withdrawal date. For subjects who enter the

period, defined as starting on the day of enrolment visit in the LTE study and ending on the Week 104 date.

EOT visit of the predecessor studies is on the same date of the enrolment visit of the LTE study unless some delays. Data collected at EOT visit of the predecessor studies prior to the first dose of IP in the LTE study will be included in the predecessor period.

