3.2.2 Adverse events – general

Adverse events (AEs) experienced by any subject at any time during the entire study will be coded using the latest version of the Medical Dictionary for Regulatory Activities (MedDRA) at the time of the primary database lock. This version of MedDRA will also be used during the final database lock.

AEs will be categorised for analysis according to their onset date into the following study periods for the SAF and SAF-LTE analysis sets:

- AEs occurring during screening/run-in period: date of Visit 1 in the predecessor study ≤
 AE onset date < date of first dose of IP in the predecessor study
- AEs occurring during on-treatment period: date of first dose of IP \leq AE onset date \leq minimum (date of last dose of IP + 33 days, date of death, date of study withdrawal)
- AEs occurring during post-treatment/follow-up period (for subjects still being followed up then): date of last dose of IP + 33 days < AE onset date ≤ study completion or withdrawal date
- AEs occurring during on-study period: date of first dose of IP ≤ AE onset date ≤ study completion or withdrawal date.

In addition, AEs will be further categorised for analysis for the on-treatment and on-study periods by the predecessor and LTE time periods as defined in Section 3.1.5.1.

If the AE has a completely missing (and unresolvable) onset date, then the AE will be assumed to have occurred during the on-treatment period, unless the end date indicates unambiguously that the AE resolved before treatment started. If the AE has a partially missing (and unresolvable) onset date, then the AE will also be assumed to have occurred during the on-treatment period, unless either the end date indicates unambiguously that the AE resolved before treatment started, or the partial onset date is in the month/year prior to start of treatment.

For each treatment group, exposure adjusted incidence rates will be defined as the number of subjects reporting adverse events divided by total exposure duration for that treatment group.

For individual subjects, exposure duration (days) for each time period is derived using the start date and end date defined for the on-treatment and on-study period in Section 3.1.5.1. The total exposure duration (years) for a treatment group will be derived as the sum of the individual subject exposure duration (days) for that treatment group and divided by 365.25.

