4.5 Safety and tolerability

4.5.1 Adverse events

AEs will be summarised separately for the on-treatment and on-study periods as defined in Section 3.2.2 unless stated otherwise. All AE summaries will be presented by analysis set and treatment groups as follows:

- SAF (Randomised Tezepelumab and Randomised Placebo), overall only
- SAF-LTE (Tezepelumab Predecessor+Tezepelumab LTE and Placebo Predecessor+Placebo LTE), overall and by time period
- SAF-LTE (Placebo Predecessor+Tezepelumab LTE), predecessor and LTE periods

All AEs will be listed for the SAF-LTE analysis set. AEs occurring during the screening/runin period or occurring post-treatment will be highlighted with an asterisk in the listing, but
not summarised separately. In addition, for subjects with a delay between the predecessor
study EOT visit and LTE study Visit 1, a listing of AEs starting more than 33 days after the
last dose of IP in the predecessor study but prior to Visit 1 in the LTE study will be provided.
A further listing of AEs occurring between the LTE study Visit 1 and the date of first dose in
the LTE study will be provided for those subjects who do not receive their first dose of IP in
the LTE study at Visit 1 of the LTE study. Information related to the outcome of any
pregnancies will also be listed for the SAF-LTE analysis set.

For each of the summaries below, the following will be included:

- Number and percentage of subjects reporting at least one AE.
- Exposure adjusted incidence rates (as defined in Section 3.2.2) per 100 subject-years

An overall summary table will be produced showing the following categories: any AEs, serious adverse events (SAEs), AEs with a fatal outcome, and AEs leading to discontinuation of IP (DAEs).

All AEs will be summarised by system organ class (SOC) and preferred term (PT) assigned to the event using the MedDRA dictionary. For each PT, for the number of subjects reporting at least one occurrence of the event, subjects with multiple occurrences of the same PT will only be counted once for the calculation of incidence rates.

Similar summaries by SOC and PT will also be presented for:

- SAEs
- Fatal AEs
- DAEs on-treatment period only

- DAEs causally related to IP on-treatment period only
- SAEs leading to discontinuation of IP on-treatment period only
- Each AESI category separately on-treatment period only

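### The first-LTE-dose day belongs to both the predecessor and LTE periods, so an AE starting that day in a placebo-to-tezepelumab switcher is counted under both treatments in the supportive by-period tables

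*SAP*

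**What the plan says.** **Period boundaries (SAP 3.1.5.1).** For subjects entering the LTE study, the predecessor on-treatment period for safety runs from the "date of first dose of IP (safety) and ending on the enrolment visit in LTE study for subjects enrolling into the LTE study". The predecessor on-study period ends on the same visit. The LTE counterpart reads "On-treatment period: starting on the day of the enrolment visit in the LTE study and ending on the date of the on-treatment period", with the end date taken from 3.1.5. The section states that the predecessor EOT visit, the LTE enrolment visit and the first LTE dose usually fall on one day; Protocol 4.1 agrees. If dosing is delayed, "the predecessor period definitions below include all data up to the day of the first dose of IP in the LTE study", and the LTE period starts from that day.

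**Same-day text.** 3.1.5.1 places EOT-visit data in the predecessor period, including "Data collected at EOT visit of the predecessor studies prior to the first dose of IP in the LTE study". SAP 3.2.1 recognises that one date can end one period and start the next: it counts that date in both for by-period exposure, and once overall.

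**AE assignment (SAP 3.2.2).** Events are classified by onset date, and "AEs will be further categorised for analysis for the on-treatment and on-study periods by the predecessor and LTE time periods as defined in Section 3.1.5.1". The other AE boundaries are strict. A run-in event needs "AE onset date < date of first dose of IP in the predecessor study", and a post-treatment event needs "date of last dose of IP + 33 days < AE onset date".

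**Output.** SAP 4.5.1 plans AE summaries for "SAF-LTE (Placebo Predecessor+Tezepelumab LTE), predecessor and LTE periods". Table 10 ticks this by-period column for each AE summary, including each AESI category and the further injection-site-reaction summaries.

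**The concern.** The predecessor/LTE boundary is the only AE boundary in 3.2.2 where one onset date qualifies for both sides. For subjects who stay on the same treatment this is cosmetic, because both columns carry that treatment. For switchers the two columns are placebo and tezepelumab, so a reaction to the first tezepelumab injection would also be printed as a placebo-period event.

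Same-day onset is most plausible for injection site reactions and hypersensitivity-type events. Protocol 6.2 requires observation after the first two DESTINATION doses for acute reactions, and SAP 8.1.7 counts an injection site reaction by whether its onset date falls in the relevant period. For post-dose events the error runs one way: it raises the placebo-period figure and narrows the apparent difference between the two columns.

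**Working it through.** **1. Apply the windows as written.** Take a subject on schedule: first predecessor dose on day 1, first LTE dose on day 365, last dose on day 701, so the on-treatment period ends on day 701 + 33 = 734.

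| AE onset | Predecessor (days 1–365) | LTE (days 365–734) |
|---|---|---|
| Day 364 | yes | no |
| Day 365 (first LTE dose) | **yes** | **yes** |
| Day 366 | no | yes |

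Period lengths are 365 and 734 − 365 + 1 = 370 days. Their sum is 735, against 734 overall, so exactly one day is shared. A delayed first dose moves the shared day to the dose date but does not remove it.

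**2. Could the data order event and dose?** Protocol 8.3.4 lists AE start and stop dates with no clock time. Protocol 6.4 records both date and time for IP. AE dates alone therefore cannot show whether an event on that day came before or after the dose.

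**3. How many subjects are exposed?** The plan gives 860 + 115 = 975 entrants and a 3:1 tezepelumab:placebo split, with placebo subjects re-randomised 1:1. Assuming equal rollover by arm, one quarter switch:
- D5180C00007: 860/4 = 215
- D5180C00009: 115/4 = 28.75, about 29

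**4. Denominator effect.** Days to the first LTE dose, inclusive, are 365 and 337. Switchers' placebo-period time on schedule, before dropout, is:
- D5180C00007: 215 × 365/365.25 = 214.9 subject-years; the shared day is 215/365.25 = 0.59 (1/365 = 0.27%)
- D5180C00009: 28.75 × 337/365.25 = 26.5 subject-years; the shared day is 28.75/365.25 = 0.08 (1/337 = 0.30%)

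**5. Numerator effect.** The documents give no first-dose-day risk. The range below is an assumption. Added subjects = switchers × risk; added rate per 100 subject-years = 100 × added subjects / placebo-period subject-years.

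| Assumed risk | D5180C00007 subjects | Added rate | D5180C00009 subjects | Added rate |
|---|---|---|---|---|
| 0.1% | 0.2 | 0.1 | 0.03 | 0.1 |
| 1% | 2.2 | 1.0 | 0.3 | 1.1 |
| 5% | 10.8 | 5.0 | 1.4 | 5.4 |

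For incidence rates these are upper bounds at each assumed risk, since a subject with an earlier placebo-period event of the same type adds nothing. That relief does not apply to the AESI occurrence rates, which count every event.

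**6. Apply a date-only rule.** With predecessor defined as onset < first LTE dose date and LTE as onset ≥ that date, day 364 goes to the predecessor period, and days 365 and 366 to the LTE period only. Only the shared day changes.

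**The case against.** The strongest reply is that the intent is already visible. 3.1.5.1 sends pre-dose EOT data to the predecessor period, which implies that post-dose data belong to the LTE period. The delayed-dose text reads naturally as a handover. SAP 2.1.2 stops Randomised Placebo data at the switch to tezepelumab. A careful programmer might well infer the right split. This stands as evidence of intent, but none of these texts places a post-dose AE. The two rules that address the shared date most directly, exposure in 3.2.1 and the predecessor-period start-date test for concomitant medications in 3.1.7, are inclusive.

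The second reply is that little depends on it, and much of that is correct:
- SAF-LTE analyses are supportive, and no hypotheses are tested.
- 2.1.2 lists the switcher group for durability of benefit, and no between-period safety contrast is planned.
- AE listings, listed dose times, and the onset-timing constraints and medical review for anaphylaxis (SAP 8.1.1) allow case-level checks, though they do not correct a table.
- Protocol 2.3 reports no serious allergic or anaphylactic reactions considered related to tezepelumab in Phase 2. It gives no injection-site-reaction risk.

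A reader might infer that the primary safety comparison is contaminated, or that tezepelumab reactions are hidden. The documents support neither. The primary AE presentation is Randomised Tezepelumab against Randomised Placebo, overall only, and it is affected only if the cut-off at switch is programmed to include the switch day, which 2.1.2 leaves open. Every affected event still appears in the LTE column.

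**Conclusion.** The gap is real and, followed as written, it gives a wrong entry: an event on the first tezepelumab dose day is also tabulated under placebo for switchers. The clear effect is limited to the supportive by-period Placebo Predecessor+Tezepelumab LTE tables, mainly the AESI and injection-site-reaction rows. All-AE rates barely move.

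The structural finding rests on the text alone. The figures of about 215 and 29 switchers rest on planned enrolment, 1:1 predecessor randomisation (implied by the 3:1 split) and equal rollover. The numerator effect cannot be known from the documents; the 0.1% to 5% risk only shows scale and should not be read as an estimate. The correction is worth making because it is nearly free and settles the Randomised Placebo cut-off as well.

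**What to change.** In SAP 3.2.2, for subjects dosed in the LTE study:
- Assign an AE with onset date before the first LTE dose date to the predecessor period, and one with onset on or after that date to the LTE period only. This matches the date-only rule 3.2.2 already applies to complete onset dates at the first predecessor dose. It should carry no exception for events said to have begun before the dose, because the AE dates collected cannot support one.
- End AE exposure time for the predecessor period, and for switchers within Randomised Placebo, on the day before the first LTE dose, so that numerator and denominator share a boundary. Align the by-period counting in 3.2.1 where it feeds AE rates.
- Keep the existing rules for EOT-visit data and for subjects never dosed in the LTE study.

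The cost is a short addition to the SAP and matching date conditions in the AE and exposure programs. A few events that did begin before the dose on that day will be attributed to the LTE period. About 0.3% of switchers' placebo-period time is dropped: 0.59 subject-years in D5180C00007 and 0.08 in D5180C00009.

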3.1.6 Visit windows

All summaries and analyses, both efficacy and safety, which are presented by time point (e.g., "Week 104") will use study period (Predecessor, LTE, and a visit window to classify the data record, which is derived from the assessment date relative to the reference start date. This approach allows appropriate classification of visits which may have occurred significantly earlier or later than the protocol assessment schedule, as well as the use of data captured at visits which have no fixed timing (notably the IPD visit), and the handling of data captured at visits for which the database label is incorrect and unresolvable.

Nominal database visit numbers will not be used in any summary or analysis by visit.

For safety variables, the reference start date is the date of first dose of IP in the predecessor study, and relative day is therefore defined as:

(Date of assessment – Date of first dose of IP) + 1.

For efficacy variables, the reference start date is the date of randomisation in the predecessor study, and relative day is therefore defined as:

(Date of assessment – Date of randomisation) + 1.

Any data collected at unscheduled or repeat visits will be listed and will be included in baseline definitions (see Section 3.1.2), and in any definitions of maximum value, minimum value or last value within the relevant study period.

Data collected at unscheduled or repeat visits will also be included in visit windows, and therefore may be included in summaries or analyses by visit or used in any sensitivity analyses which involve imputation of data from subjects with non-missing values to subjects with missing values. In the case of a missing value at a scheduled visit, which is then followed by a non-missing value at an unscheduled or repeat assessment within the same visit window, the non-missing value at the unscheduled/repeat assessment will replace the missing value at the scheduled visit.

[figure not shown]
If a subject has more than one non-missing value within the same visit window, the following rules will apply:

- The non-missing value closest to the target day will be selected for analysis at that visit.
- If two non-missing values are the same distance from the target day, the earlier of the two values will be selected for analysis at that visit.
- If two non-missing values are recorded on the same day and have a different assessment time associated with both of them, the value with the earliest assessment time will be selected for analysis at that visit.
- If two non-missing values (for continuous variables) are recorded on the same day and have no assessment time associated with at least one of them, or the same assessment time associated with both of them, the average of the two values will be selected for analysis at that visit. For categorical variables in this situation, the worst case will be used.

If a subject has no value within a particular visit window, then the subject will have a missing value at that visit in summaries and analysis.

The same visit window definitions below will be used regardless of whether the planned treatment period or the on-treatment period is used for analysis (see Section 3.1.5). In practice, each data record in the planned treatment period will be first identified, and then further flagged according to whether it is on-treatment or off-treatment. This flag will be used to select all eligible records for subsequent visit windowing, according to whether the derived visits are to be used in a planned treatment period or an on-treatment period analysis. It should be noted that, if treatment was discontinued within a particular visit window, the rules above for handling multiple values within the same visit window could select a different record according to whether a planned treatment period analysis or an on-treatment period analysis is needed.

Table 3 summarises the visit windows to be used in analyses as follows:

• "Visit Window 3" will be used for weight, height (adolescents in Study D5180C00007 only),

Table 3Visit windows

[figure not shown]
| Time Point | Target | Visit Window 1 | | Visit Window 2 | | Visit Window 3 | | |
|------------------------|--------|--|-----------------|-----------------|-----------------|-----------------|-----------------|--|
| Time Font | Day | D5180 C00007 | D5180 C00009 | D5180 C00007 | D5180 C00009 | D5180 C00007 | D5180 C00009 | |
| Baseline (Week 0) | 1 | See Section 3.1.2 for baseline definitions | | | | | | |
| Week 2 | 15 | 2-21 | N/A | 2-21 | N/A | - | | |
| Week 4 | 29 | 22-42 | 2-42 | 22-42 | 2-42 | N/A | 2-56 CCI | |
| Week 8 | 57 | 43 | -70 | 43- | -70 |  | | |
| Week 12 | 85 | 71-98 | | 71-98 | | - | | |
| Week 16 | 113 | 99- | 99-126 99-126 | | 126 | - | | |
| Week 20 | 141 | 127-154 127-154 | | -154 | - | | | |
| Week 24 | 169 | 155-182 | | 155-182 | | 141-196 | | |
| Week 28 | 197 | 183-210 | | 183-210 | | - | | |
| Week 32 | 225 | 211-238 | | 211-238 | | - | | |
| Week 36 | 253 | 239-266 | | 239-266 | | - | | |
| Week 40 | 281 | 267-294 | | 267-294 | | - | | |
| Week 44 | 309 | 295-322 | | 295 | 295-322 | | - | |
| Week 48 | 337 | 323-350 | | 323-350 | | N/A | 309-364 | |
| Week 52 | 365 | 351-378 | | 351-378 | | 337-392 | N/A | |
| Follow-up Week 54 a | 379 | N/A | 351-399 | N/A | 351-399 | N | /A | |
| Week 56 | 393 | 379 | -406 | | | | - | |
| Follow-up Week 58 a | 407 | 386-427 | N/A | 386-427 | N/A | N | /A | |
| Follow-up Week 60 a | 421 | N/A | 400-441 | N/A | 400-441 | N | /A | |
| Week 60 | 421 | 407 | -434 | | - | | - | |

| Time Point Target | | Visit Window 1 | | Visit Window 2 | | Visit Window 3 | |
|------------------------|-----|-----------------|-----------------|-----------------|-----------------|-----------------|-----------------|
| Time Tomic | Day | D5180 C00007 | D5180 C00009 | D5180 C00007 | D5180 C00009 | D5180 C00007 | D5180 C00009 |
| Follow-up Week 64 a | 449 | 428-469 | N/A | 428-469 | N/A | N | /A |
| Week 64 | 449 | 435-462 | | 379-490 | | - | |
| Week 68 | 477 | 463-490 | | - | | - | |
| Week 72 | 505 | 491-518 | | - | | - | |
| Week 76 | 533 | 519-546 | | 491-574 | | 393-630 | 365-630 |
| Week 80 | 561 | 547-574 | | - | | - | |
| Week 84 | 589 | 575-602 | | - | | - | |
| Week 88 | 617 | 603-630 | | 575-672 | | | - |
| Week 92 | 645 | 631-658 | | - | | | |
| Week 96 | 673 | 659-686 | | - | | | |
| Week 100 | 701 | 687-714 | | - | | - | |
| EOT Week 104 | 729 | 715-749 | | 673-770 | | 631-812 | |
| Follow-up Week 110 | 771 | 750-791 | | - | | - | |
| Follow-up Week 116 | 813 | 792-833 | | 771-896 | | | - |

^a Only applicable for subjects who do not enrol into the LTE study.

| Time Point | Tanget Day | | Visit Window 2 | 2 |
|--------------------|------------|-----|----------------|------------|
| Time Point | Target Day | CCI | | Urinalysis |
| EOT Week 104 | 729 | | | 673-854 |
| Follow-up Week 110 | 771 | | | - |

In all cases above, no time points will be presented in summary tables or included in statistical analysis which do not correspond to the time points scheduled in the protocol for the variable in question. Listings of data will include all scheduled and unscheduled visits.

